For subjects who are on oral steroids at the Baseline, their steroid dose must be tapered off for 4 weeks (until Week 4) and withdrawn for the rest of the study period. For subjects who are on cyclosporine at the Baseline, the treatment must be tapered off for 8 weeks (until Week 8) and withdrawn for the rest of the study period.

Throughout the study, subjects who are on etretinate (maximum dose of 20 mg/day at the Baseline), MTX, azathioprine, or salazosulfapyridine will be continued on their stable dose or have their dose of GPP-specific concomitant medications decreased as specified in Section [5.2.3.2](#). Dose escalation is not allowed for these treatments.

No study drug will be administered at the final visit.

70-Day Follow-Up/Premature Discontinuation

Subjects may discontinue adalimumab treatment at any time during study participation (Section [5.4](#)). Subjects who end study participation early will have a premature discontinuation (PD) Visit. All subjects will have a follow-up phone call approximately 70 days after the last administration of study drug to obtain information on any new or ongoing AEs.

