5.2.2 Exclusion Criteria

1. Subject has erythrodermic psoriasis, guttate psoriasis, or subcorneal pustular dermatosis at Screening.
2. Subject diagnosed drug-induced GPP.
3. Total score of 14 or more in JDA severity index of GPP in GPP Medical Care Guideline 2014 in Japan.
4. Subject has other active skin disease (e.g., urticarial, atopic dermatitis) or skin infections (bacterial, fungal, or viral) that may interfere with evaluation of GPP, with the exception of footpad trichophytosis (athlete's foot).
5. Subject who cannot taper off cyclosporine until Week 8 after the Baseline and during the study. Subjects who cannot taper etretinate to 20 mg/day at the maximum dose prior to the Baseline.
6. Subject who is receiving oral corticosteroid more than 10 mg/day at the Baseline, and cannot taper off until Week 4 after the Baseline and during study.
7. Subject who received granulocyte and monocyte adsorption apheresis (GMA) therapy for at least 28 days prior to the Baseline and cannot avoid this therapy during the study.
8. Subjects who received any investigational agents of chemical or biologic nature (including anti-IL17 agents), which would be efficacious to GPP or psoriasis-related skin disease for at least 28 days or 5 half-lives of the drug prior to the Baseline, whichever is longer, and during the study.
9. Subjects who received ustekinumab for at least 84 days prior to the Baseline and during the study.
10. Subject who cannot avoid PUVA or narrow-band UVB phototherapy for at least 14 days prior to the Baseline and during the study.
11. Subject who cannot avoid "Strongest" corticosteroid in Japanese classification of topical therapy for at least 14 days prior to the Baseline and during the study.

12. Subject who cannot avoid anti-tumor necrosis factor (TNF) agent other than infliximab and adalimumab (including but not limited to etanercept [Enbrel], golimumab [Simponi] or certolizumab pegol [Cimzia]) for at least 28 days prior to the Baseline and during the study.
13. Prior exposure to adalimumab.
14. Subject who has previous used infliximab:
 - and has not clinically responded at any time ("primary non-responder") unless subject experienced a treatment limiting reaction, or
 - who used infliximab ("secondary treatment failure") within 42 days prior to the Baseline.

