5.2.3.2 Concomitant Therapy

Doses of etretinate (tapered to 20 mg/day at maximum dose prior to the Baseline), MTX, azathioprine, or salazosulfapyridine taken at Baseline will be continued and remain stable throughout the study. Doses may be decreased or terminated in the event of moderate-to-severe treatment-related toxicities or improvement of GPP skin lesion according to the discretion of the investigator. Dose escalation of these treatments will not be allowed.

Doses of topical corticosteroids ("Very strong," "Strong," "Medium" and "Weak" in Japanese classification), topical vitamin D3, or topical tacrolimus taken at the Baseline will be continued without dose escalation. Dose escalation (increase of amount for use) of topical corticosteroids is allowed only to use lower classes of drugs. Doses may be decreased or terminated in the event of moderate-to-severe treatment-related toxicities or improvement of GPP skin lesion according to the discretion of the investigator.

For subjects who are on oral steroids at the Baseline, their steroid dose must be tapered off for 4 weeks (until Week 4) and withdrawn for the rest of the study period. For subjects

who are on cyclosporine at the Baseline, the treatment must be tapered off for 8 weeks (until Week 8) and withdrawn for the rest of the study period.

Changes in all concomitant medications will be assessed at each study visit from Baseline (Week 0) through Week 52/PD Visits. Any changes will be documented, including the reason for the change of dose will be documented in the source documents and captured on the appropriate eCRF page.

Prophylaxis treatment with isoniazid for TB will be recorded. Even if a subject prematurely discontinues the study, isoniazid treatment should be continued for 9 months considering the best interest of the subject at the discretion of the investigator.

Any vaccine (except for live vaccines) administered during the study will be recorded in the eCRF as a concomitant medication.

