5.3.3.2 Secondary Variables

Secondary efficacy variables, to be analyzed at each scheduled visit, include:

1. Proportion of subjects achieving Clinical Response (expect Week 16, which is the primary endpoint).
2. Proportion of subjects achieving remission.
3. Change from the Baseline in total GPP score (skin and systemic/laboratory test).
4. Change from the Baseline in JDA severity index of GPP.
5. Change and Percent change from the Baseline in total skin score.
6. Change from the Baseline in total systemic/laboratory test score.
7. Change from the Baseline in score of erythema area (overall) and BSA (BSA of GPP).
8. Change from the Baseline in score of erythema area with pustule and BSA.
9. Change from the Baseline in score of edema area and BSA.
10. Change from the Baseline in Body temperature.
11. Change from the Baseline in WBC.
12. Change from the Baseline in hs-CRP.
13. Change from the Baseline in serum Albumin.
14. Proportion of subjects achieving "Mild" in JDA severity index of GPP for patients with "Moderate" or "Severe" at the Baseline.
15. Proportion of subjects achieving Treatment Success in PGA (reduction of 2 grades).
16. Change from the Baseline in PGA grade.
17. Proportion of subjects achieving PGA 0/1 for patients with PGA grade at least 2 at Baseline.
18. Proportion of subjects achieving PASI 90.

19. Proportion of subjects achieving PASI 75.
20. Proportion of subjects achieving PASI 50.
21. Change and Percent change from the Baseline in PASI score.
22. Proportion of subjects achieving DLQI = 0.
23. Change from the Baseline in DLQI score.
24. Change from the Baseline in SF-36 score.
25. Proportion of subjects taking systemic co-medication for GPP (etretinate, MTX).
26. Proportion of subjects taking topical co-medication for GPP (corticosteroid, vitamin D3, tacrolimus).

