6.3 Toxicity Management

Subjects who develop a new infection while undergoing treatment with adalimumab should be monitored closely. Administration of study injections should be interrupted if a subject develops an infection requiring IV anti-infective treatment or if an infection meets the definition of "serious" (see Section 6.1.1.2 for definitions). Study medication may be

restarted once the physician determines that the infection has been successfully treated. Otherwise prohibited concomitant medications may be given if medically necessary. Prior to use, every attempt should be made to contact the AbbVie Study Physician for direction on re-introduction of adalimumab therapy after prohibited medication administration.

If the subject must undergo elective surgery, the study injections must be interrupted 2 weeks prior to the surgery. If the subject must undergo emergency surgery, the study injections must be interrupted at the time of the surgery. The injectable study medication can recommence at least 2 weeks after surgery once the physician has examined the surgical site and determined that it has healed and there is no sign of infection.

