10.3 Secondary Efficacy Analyses

Discrete variables will be summarized by counts and percentages, and continuous variables will be summarized by descriptive statistics on the items below at each visit.

The subjects who have missing data for any reason such as early terminated subjects will be included into analysis using NRI for discrete variables or LOCF for continuous variables.

- Proportion of subjects achieving Clinical Response (expect Week 16, which is the primary endpoint).
- Proportion of subjects achieving remission.
- Change from the Baseline in total GPP score (skin and systemic/laboratory test).
- Change from the Baseline in JDA severity index of GPP.
- Change and Percent change from the Baseline in total skin score.
- Change from the Baseline in total systemic/laboratory test score.
- Change from the Baseline in score of erythema area (overall) and BSA (BSA of GPP).
- Change from the Baseline in score of erythema area with pustule and BSA.
- Change from the Baseline in score of edema area and BSA.
- Change from the Baseline in Body temperature.
- Change from the Baseline in WBC.
- Change from the Baseline in hs-CRP.
- Change from the Baseline in serum Albumin.
- Proportion of subjects achieving "Mild" in JDA severity index of GPP for patients with "Moderate" or "Severe" at the Baseline.
- Proportion of subjects achieving Treatment Success in PGA (reduction of 2 grades).
- Change from the Baseline in PGA grade.
- Proportion of subjects achieving PGA 0/1 for patients with PGA grade at least 2 at Baseline.
- Proportion of subjects achieving PASI 90.

- Proportion of subjects achieving PASI 75.
- Proportion of subjects achieving PASI 50.
- Change and Percent change from the Baseline in PASI score.
- Proportion of subjects achieving DLQI = 0.
- Change from the Baseline in DLQI score.
- Change from the Baseline in SF-36 score.
- Proportion of subjects taking systemic co-medication for GPP (etretinate, MTX, oral steroids, cyclosporine).
- Proportion of subjects taking topical co-medication for GPP (corticosteroid, vitamin D3, tacrolimus).

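### SAP 10.3 pools two drugs that the protocol itself withdraws into the systemic co-medication efficacy proportion, so part of any fall may be mandated rather than response-driven

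*SAP*

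**What the plan says.** The protocol's secondary variable (5.3.3.2, item 25; the synopsis agrees) reads "Proportion of subjects taking systemic co-medication for GPP (etretinate, MTX"). The SAP's counterpart in 10.3 reads "Proportion of subjects taking systemic co-medication for GPP (etretinate, MTX, oral steroids, cyclosporine"). SAP 10.3 summarises its items at each visit, and SAP 10.1 attaches exact 95% confidence intervals to proportions. SAP section 12 does not mention the longer drug list.

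The protocol treats the two pairs of drugs differently:

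- **Oral steroids at Baseline:** "their steroid dose must be tapered off for 4 weeks (until Week 4) and withdrawn for the rest of the study period" (5.2.3.2, also 5.1).
- **Cyclosporine at Baseline:** "the treatment must be tapered off for 8 weeks (until Week 8) and withdrawn for the rest of the study period" (5.1, also 5.2.3.2).
- **Etretinate and MTX:** kept stable. The investigator may reduce or stop them for toxicity or because the skin lesions improve. They may not go up: "Dose escalation of these treatments will not be allowed" (5.2.3.2). Nothing forces them to stop.

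The exclusion criteria reinforce the taper. Criterion 5 excludes a "Subject who cannot taper off cyclosporine until Week 8 after the Baseline and during the study". Criterion 6 excludes a "Subject who is receiving oral corticosteroid more than 10 mg/day at the Baseline, and cannot taper off until Week 4" after Baseline.

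**The concern.** Stopping etretinate or MTX can carry information about response, because improvement is one of the permitted reasons. Stopping oral steroids or cyclosporine on the protocol's timetable carries none, because it is required of responders and non-responders alike. Pooling the four drugs in one proportion mixes the two kinds of change.

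The trial has one open-label arm, so no control group would show the mandated part on its own. A table whose pooled figure drops after Week 4 and Week 8 could be taken as evidence that adalimumab spares steroids or cyclosporine, when some or all of the drop was written into the protocol.

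**Working it through.** The documents give no figure for this variable, so there is nothing to reproduce. Their power figures concern the primary endpoint only.

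**Inputs**

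- N = 10, the target sample size (SAP 4.3, protocol 8.2).
- b = subjects on etretinate and/or MTX at Baseline. Not given; assumed.
- k = subjects on oral steroids and/or cyclosporine, but on neither etretinate nor MTX, at Baseline. Not given; assumed.
- Assumptions: adalimumab has no effect on co-medication, the taper is fully followed, etretinate and MTX use does not change, and no data are missing.

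**Formulas**

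- SAP list: Baseline (b + k)/N; after Week 8, b/N; forced fall k/N.
- Protocol list: b/N at both times; forced fall 0.

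With N = 10 the forced fall under the SAP list is 10k percentage points. For b = 4:

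| k | SAP list, Baseline | SAP list, after Week 8 | Fall, SAP list | Fall, protocol list |
|---|---|---|---|---|
| 0 | 40% | 40% | 0 points | 0 points |
| 1 | 50% | 40% | 10 points | 0 points |
| 2 | 60% | 40% | 20 points | 0 points |
| 3 | 70% | 40% | 30 points | 0 points |
| 5 | 90% | 40% | 50 points | 0 points |

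The fall does not depend on b. With b = 0 and k = 3 the SAP proportion goes from 30% to 0%. In the k = 3 row the exact 95% intervals are 34.8% to 93.3% for 7/10 and 12.2% to 73.8% for 4/10. They describe sampling error and do not reveal that the drop was mandated.

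**How likely is k of at least 1?** Let q be the chance that a subject enters on these drugs alone, independently between subjects. Then P(k ≥ 1) = 1 − (1 − q)^10 and the expected forced fall is 100q points. For assumed q:

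- 5%: 40%, expected fall 5 points
- 10%: 65%, 10 points
- 20%: 89%, 20 points
- 30%: 97%, 30 points

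**Two details of timing and coding**

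- SAP Table 2 sets the Week 8 window at Days 44 to 71, so a Week 8 record may precede the end of the cyclosporine taper. The full forced fall should appear from the Week 12 window on.
- SAP 6.5 codes missing binary data as not achieved, without saying whether that means taking or not taking co-medication. If it means not taking, dropouts also lower the proportion: 4/10 users with 2 of them missing becomes 2/10. The table above leaves this out.

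**The case against.** The strongest reply has five parts.

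1. **The fall is conditional.** A reader might infer that the endpoint must improve even if adalimumab does nothing. The documents do not support that. If every steroid or cyclosporine user also takes etretinate or MTX, or nobody enters on these drugs, the pooled fall is 0. Inclusion criterion 4 requires failure of, intolerance to or a contraindication to approved treatment, and protocol 3.0 counts cyclosporine as approved, so low use at entry is plausible. This stands.

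2. **Later use can be informative.** A reader might infer that any steroid or cyclosporine use after Week 8 is merely a deviation. That does not follow. Protocol 6.3, in its text on infections, says "Otherwise prohibited concomitant medications may be given if medically necessary". Under 5.4.1, prohibited medication leads to withdrawal only where continuing study drug would put the subject at risk. Continued or restarted use may signal uncontrolled disease, so removing the two drugs from view would lose efficacy information. This stands and shapes the fix.

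3. **Etretinate and MTX are not a pure measure of response.** They may be cut for toxicity and may not be raised. True: the protocol's list removes the forced part but does not isolate a drug effect.

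4. **The layout is not fixed.** SAP 10.3 does not rule out one row per drug, and SAP 7.3 already counts concomitant therapy by generic name. But 10.3 does not ask for separate rows either, and 7.3 does not say by visit.

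5. **No claim is planned.** Neither document claims a steroid- or cyclosporine-sparing effect, and SAP 10.1 keeps the analysis descriptive. This limits the harm to misreading.

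A reader might also infer that the SAP widened the protocol's definition without authority. That cannot be settled. The SAP follows a protocol dated 06 April 2017 with four administrative changes, while the supplied synopsis is dated 08 June 2015, so the wording may have entered in between. The pooling problem is the same either way.

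**Conclusion.** The point holds in conditional form. As written, the SAP's pooled proportion contains a component that the protocol drives to zero regardless of response, and the single-arm design cannot separate that component from a drug effect. The forced fall is 10 percentage points per subject who enters on oral steroids and/or cyclosporine without etretinate or MTX: 0 for k = 0, 20 points for k = 2, 50 points for k = 5. This rests on N = 10, full compliance, no missing data, no drug effect and unchanged etretinate and MTX use. Because k is unknown, the documents support a possible built-in fall of this size, not a certain one.

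The variable is secondary, descriptive and untested, so the primary result and power do not change. It is worth correcting because the correction is cheap and, with so few subjects, each one moves the figure by 10 points.

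**What to change.** - In SAP 10.3, define the pooled efficacy proportion as in protocol item 25: etretinate and MTX.
- Report oral steroids and cyclosporine by visit in separate rows, one per drug, with a footnote that the protocol requires their withdrawal by Week 4 and Week 8 respectively.
- Count use after those weeks separately, as continued or restarted use, so that rescue stays visible.
- Record the chosen definition in SAP 12.1.

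The cost is a wording change and one split table, from data already collected. The reported fall in systemic co-medication may be smaller. No dose, taper or other clinical rule changes.

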10.4 Handling of Multiplicity

No adjustment for multiplicity will be done.

10.5 Efficacy Subgroup Analysis

The subgroup analysis listed below is planned for the subgroups shown. Proportion of subjects achieving Clinical Response (remission and improvement) at Weeks 16, 24, and 52.

- Dose escalation: (without dose escalation, with dose escalation)
- Previous infliximab experience (infliximab naïve, prior exposure to infliximab)

For all subject in Dose Escalation Set will be summarized as:

- Proportion of subject achieving Clinical Response by dose escalation.

11.0 Safety Analysis

11.1 General Considerations

Unless otherwise specified, all safety analysis will be performed on the Safety dataset.

11.2 Analysis of Adverse Events

11.2.1 Treatment-Emergent Adverse Events

Treatment-emergent adverse events (TEAEs) are defined as events that begin or worsen either on or after the first dose day of the study medication and within 70 days after the last dose of the study medication. Treatment-emergent AEs will be summarized separately for the first half period (Week 0 to Week 24), the second half period (Week 24 to Week 52), and entire period (Week 0 to Week 52).

For the interim analysis at Week 24, treatment-emergent adverse events are defined as any event with an onset or worsening on or after the first dose of study drug and on or prior to the Week 24 dosing date for subjects who continued in the study after Week 24, and up to 70 days after the last dose of study drug for subjects who discontinued prior to Week 24 visit.

Treatment-emergent adverse events will be summarized and presented using primary Medical Dictionary for Regulatory Activities (MedDRA) system organ classes (SOCs) and preferred terms (PTs) according to the version of the MedDRA coding dictionary used for the study at the time of database lock. The actual version of the MedDRA coding dictionary used will be noted in the clinical study report. The system organ classes will be presented in alphabetical order and the preferred terms will be presented in alphabetical order within each system organ class.

For the Dose Escalation set, TEAEs will be reported before the date of dose escalation and also on or after the date of dose escalation, separately.

Adverse Event Overview

The number and percentage of subjects experiencing treatment-emergent adverse events will be summarized for the following adverse event categories.

- Any treatment-emergent adverse event

- Any treatment-emergent adverse event that was rated as possibly related to study drug by the investigator (Reasonable Possibility)
- Any treatment-emergent severe adverse event
- Any treatment-emergent serious adverse event
- Any treatment-emergent adverse event leading to discontinuation of study drug
- Any treatment-emergent serious adverse event that was rated as possibly related to study drug by the investigator (Reasonable Possibility)
- Any treatment-emergent adverse event leading to death
- Any treatment-emergent adverse event of special interest
- Any Deaths

Adverse Events by SOC and PT

The number and percentage of subjects experiencing adverse events will be tabulated according to the primary MedDRA system organ class (SOC) and preferred term (PT). Subjects reporting more than one adverse event for a given MedDRA PT will be counted only once for that term (most severe incident for the severity tables and most related incident for the relationship tables). Subjects reporting more than one type of adverse event within a MedDRA SOC will be counted only once for that SOC. Subjects reporting more than one type of adverse event will be counted only once in the overall total.

The following AEs will be summarized using the conventions described above:

- Any treatment-emergent adverse event
- Any treatment-emergent adverse event that was rated as possibly related to study drug by the investigator (Reasonable Possibility)
- Any treatment-emergent adverse event by maximum severity
- Any treatment-emergent adverse event by maximum relationship to study
- Any treatment-emergent serious adverse event
- Any treatment-emergent adverse event leading to discontinuation of study drug

- Any treatment-emergent serious adverse event that was rated as possibly related to study drug by the investigator (Reasonable Possibility)
- Any treatment-emergent adverse event leading to death
- Any treatment-emergent adverse event of special interest

Adverse Events by Maximum Severity

Adverse events will also be summarized by maximum severity. If a subject has an adverse event with unknown severity, then the subject will be counted in the severity category of "unknown," even if the subject has another occurrence of the same adverse event with a severity present. The only exception is if the subject has another occurrence of the same adverse event with the most extreme severity – "Severe." In this case, the subject will be counted under the "Severe" category.

Adverse Events by Maximum Relationship

Adverse events will also be summarized by maximum relationship to study, as assessed by the investigator. If a subject has an adverse event with unknown relationship, then the subject will be counted in the relationship category of "unknown," even if the subject has another occurrence of the same adverse event with a relationship present. The only exception is if the subject has another occurrence of the same adverse event with a relationship assessment of "Reasonable Possibility." In this case, the subject will be counted under the "Reasonable Possibility" category, respectively.

Adverse Event Rates per 100 Patient Years of Study Drug Exposure

Incidence rates per 100 patient years of exposure to study drug will be presented for adverse event overviews and for adverse events by SOC and PT.

The treatment-emergent adverse event rate per 100 patient years of exposure will be calculated overall, for each primary SOC, and each PT. For this calculation, 1 year will be considered to be 365.25 days. The numerator of the overall rate, the SOC rate, or the PT rate, will be the total number of treatment-emergent adverse events reported overall,

for the SOC, or for the PT, respectively; i.e., a subject can be counted more than once overall, for a SOC, and for a PT. The denominator of the rates will be the total number of days exposed to study drug summed across all treated subjects divided by 365.25, and rounded to one decimal place. The adverse event rate per 100 subject-years of exposure will be calculated as [(numerator/denominator)]*100. The number of adverse events reported (numerator), the total number of years of study drug exposure (denominator), and the adverse event rate per 100 subject-years will be presented overall, for each SOC, and for each PT.

Adverse Events of Special Interest (AESI)

The analysis of treatment-emergent adverse events of special interest based on Standardized MedDRA Queries (SMQs) or Company MedDRA Queries (CMQs) will be presented for the adverse event overviews and for adverse events by SOC and PT.

The final analyses will follow the latest version of Product Safety Statistical Analysis Plan (PSSAP).

The current list of AEs of special interest in PSSAP (version 5.0, dated 20Jan2016) for treatment with adalimumab is:

- Any Infections AE
- Any Serious Infection AE
- Any Legionella Infection AE
- Any Diverticulitis AE
- Any Opportunistic Infection AE (Excluding Oral Candidiasis and TB)
- Any Oral Candidiasis AE
- Any Tuberculosis AE
- Any Active Tuberculosis AE
- Any Latent Tuberculosis AE
- Any Parasitic Infection AE
- Any Reactivation of Hepatitis B AE
- Any Progressive Multifocal Leukoencephalopathy (PML) AE
- Any Malignancy AE

- Any Lymphoma AE
- Any Hepatosplenic T-Cell Lymphoma AE (HSTCL)
- Any Non-Melanoma Skin Cancer (NMSC) AE
- Any Melanoma AE
- Any Leukaemia AE
- Any Other Malignant AE (Excluding NMSC, Melanoma, Lymphoma, HSTCL, and Leukemia)
- Any Allergic Reaction AE (Including Angioedema/Anaphylaxis)
- Any Lupus-Like Reactions and Systemic Lupus Erythematosus AE
- Any Vasculitis AE
- Any Cutaneous Vasculitis AE
- Any Non-Cutaneous Vasculitis AE
- Any Sarcoidosis AE
- Any Autoimmune Hepatitis AE
- Any Myocardial Infarction Related AE
- Any Cerebrovascular Accident Related AE
- Any Congestive Heart Failure Related (CHF) AE
- Any Pulmonary Embolism Related AE
- Any Interstitial Lung Disease AE
- Any Intestinal Perforation AE
- Any Pancreatitis AE
- Any Stevens-Johnson Syndrome AE
- Any Erythema Multiforme Related AE
- Any Worsening/New Onset of Psoriasis AE
- Any Demyelinating Disorder AE (Including Multiple Sclerosis, Guillain-Barré Syndrome, and Optic Neuritis and Others)
- Any Amyotrophic Lateral Sclerosis AE
- Any Reversible Posterior Leukoencephalopathy Syndrome (RPLS) AE
- Any Hematologic Disorders AE (Including Pancytopenia)

- Any Liver Failure and Other Liver Event AE (Except Gall Bladder Related Events)
- Any Humira Administration Related Medication Errors AE
- Any Injection Site Reaction AE
- Any AE Leading to Death
- Any AE Leading to Discontinuation of Study Drug
- Any Deaths

Additional AEs may be considered for tabulation/summary based on recommendations from Clinical and Safety as deemed appropriate.

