5.0 Analysis Populations

5.1 Definition for Analysis Populations

Full Analysis Set:

Full Analysis Set (FAS) population includes all subjects who complied with GCP and received at least one dose of study drug and had at least one post-treatment efficacy assessment. FAS is the primary population for the efficacy analysis. In general, efficacy analysis will be performed for all subjects regardless dose escalation.

Safety Dataset:

The Safety set consists of all subjects who received at least one injection of study drug.

Dose Escalation Dataset:

This set consists of all subjects who escalated the study dose from 40 mg eow to 80 mg eow on or after Week 8. In order to evaluate the effect of dose escalation, these subjects will be analyzed for the efficacy and safety (AEs only) using the data prior- and post-dose escalation date, separately.

Pharmacokinetic assessments will be conducted on all subjects who were administered at least one dose of study drug and have at least one post-dose sample collected for the determination of serum adalimumab concentration.

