6.0 Analysis Conventions

Unless otherwise specified, the efficacy and safety continuous variables will be summarized using the descriptive statistics (including mean, standard deviation, median, minimum and maximum), and for qualitative variables, the number (n) and percentage (%) of subjects with non-missing data per category will be the default summary presentation.

All statistical analyses will be conducted at a two-sided significance level of 0.050 or a one-sided significance level of 0.025 (when rounded to 3 decimal places).

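### If anyone stops before Week 24, the Week 24 to 52 adverse-event percentages can be distorted, because their default denominator is every subject ever dosed

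*SAP*

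**What the plan says.** SAP 11.2.1 splits TEAE summaries into Weeks 0 to 24, "the second half period (Week 24 to Week 52", and the whole 52 weeks. The overview measure is a count of subjects with a percentage: "The number and percentage of subjects experiencing treatment-emergent adverse events will be summarized for the following adverse event categories". The tables by system organ class and preferred term use the same measure.

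No denominator is written for the second half. Two general rules supply one:

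- SAP 11.1: "Unless otherwise specified, all safety analysis will be performed on the Safety dataset".
- SAP 5.1: "The Safety set consists of all subjects who received at least one injection of study drug".

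An event stays treatment-emergent if it begins or worsens "within 70 days after the last dose of the study medication".

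SAP 11.2.1 also plans exposure-adjusted rates: "Incidence rates per 100 patient years of exposure to study drug will be presented for adverse event overviews and for adverse events by SOC and" preferred term. Their denominator is "the total number of days exposed to study drug summed across all treated subjects divided by 365.25". No split of that exposure by half is described.

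**The concern.** A percentage for a period should be taken over subjects who could have had the event in that period. Here, subjects who left before Week 24 remain in the second-half denominator by default.

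Some of them can also enter the numerator. A subject last dosed at Week 20 who has an event at Week 28 is still inside the 70-day window. By date the event falls in the second half, although the subject is off drug. Under the separate interim definition in SAP 11.2.1, the same event also belongs to the Week 24 interim analysis, because early stoppers are followed there to 70 days after the last dose.

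At stake is how the later-treatment column is read. It could suggest that fewer subjects have events with longer treatment when part of the drop comes from subjects no longer treated. It could also attribute off-drug events to continued treatment. The SAP does write a special rule where it wants one, with before-and-after TEAE reporting for the Dose Escalation set, but it writes none for the half-periods.

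**Working it through.** **Inputs**

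- N = 10 subjects, the target in SAP 4.3.
- d = subjects who stop before Week 24. The documents give no value; 0 to 4 is an assumed range.
- x = subjects treated beyond Week 24 who have a second-half TEAE (illustrative).
- y = early leavers who have a TEAE after Week 24 (illustrative).
- TEAE window: 70 days = 10 weeks after the last dose (SAP 11.2.1).

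The plan states no second-half percentage or denominator, so there is no figure of its own to reproduce.

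**Step 1: which denominator applies.** SAP 11.1 directs safety analyses to the Safety set unless something else is specified, and nothing else is specified for the second half. The general convention in SAP 6.0, "the number (n) and percentage (%) of subjects with non-missing data per category will be the default summary presentation", does not define an at-risk set for an adverse-event period. The default denominator is therefore N.

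**Step 2: dilution when leavers add no events (y = 0).** The default gives x/N and the still-treated percentage is x/(N-d), so the ratio is (N-d)/N. With x = 3:

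| d | Default, 3/10 | Still treated, 3/(10-d) | Ratio |
|---|---|---|---|
| 0 | 30.0% | 30.0% | 1.0 |
| 1 | 30.0% | 33.3% | 0.9 |
| 2 | 30.0% | 37.5% | 0.8 |
| 3 | 30.0% | 42.9% | 0.7 |
| 4 | 30.0% | 50.0% | 0.6 |

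**Step 3: which leavers can add events.** The last-dose week plus 10 gives the end of the window: Week 6 to Week 16, Week 14 to Week 24, Week 16 to Week 26, Week 22 to Week 32. Only those last dosed before about Week 14 cannot have a second-half TEAE.

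**Step 4: effect when leavers do add events.** The default becomes (x+y)/N. For d = 3 and x = 3 the still-treated figure remains 3/7 = 42.9%:

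- y = 0: 3/10 = 30.0%
- y = 1: 4/10 = 40.0%
- y = 2: 5/10 = 50.0%

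The two measures agree when y = x·d/(N-d) = 9/7, about 1.3. One such leaver leaves the table too low and two push it too high.

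**Step 5: patient-year rates.** A leaver adds only their own exposed days, so the whole-study rate is not diluted in this way. A second-half rate, however, has no defined exposure. Take 10 completers and 5 second-half events:

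- Whole-study exposure: 10 × 364/365.25 = 9.97 patient-years, so 50.2 per 100.
- Week 24 to 52 exposure: 10 × 196/365.25 = 5.37 patient-years, so 93.2 per 100.

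The SAP does not say which it would use, and this gap exists even with no dropout.

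**The case against.** The strongest reply has five parts.

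1. **The denominator is inferred, not written.** True, but it follows from the SAP's own default rule, which is what a programmer would apply.
2. **A reader might infer that long-term event rates are understated as a matter of course.** The documents do not support that. Without early leavers there is no effect, and no dropout figure is given. Off-drug events in leavers can cancel or reverse the dilution (Step 4). The measure the SAP itself calls a rate, per 100 patient-years over the whole study, is not diluted by leavers. The point is limited to percentages of subjects and is conditional.
3. **Many leavers are still under observation after Week 24.** This stands for those last dosed after about Week 14. It changes the problem from pure dilution to a mixture of on-drug and off-drug experience.
4. **Restricting the second-half table to subjects still dosed would drop some TEAEs, so the halves would no longer account for the whole.** This is a fair warning, and the fix has to show those events on their own line.
5. **The effect is small and visible.** The study is single-arm and descriptive, with about 10 subjects. Counts accompany percentages, SAP 8.0 reports discontinuation by Week 24, and SAP 11.2.2 lists every TEAE. This limits the importance, but listings do not correct a summary percentage.

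No passage says that the split is meant to compare early with late safety, and the halves are unequal (24 and 28 weeks). Raw percentages are therefore not a like-for-like comparison even without dropout.

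**Conclusion.** The point holds in a limited form. Followed as written, the plan takes second-half TEAE percentages over everyone ever dosed. If subjects leave before Week 24, those percentages can be distorted in two ways: diluted by subjects with no second-half exposure, and mixed with off-drug events from leavers inside the 70-day window.

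The relative understatement is d/10 (10% for one leaver, 20% for two, 30% for three) only if the leavers add no later events. Otherwise neither size nor direction is fixed. This rests on N = 10 and an assumed d. If d = 0 the percentages are unaffected. The practical impact is modest, but the correction is cheap and the separate late-period summary is prespecified.

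**What to change.** In SAP 11.2.1:

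- For the second-half table, take both the denominator and the events from subjects with at least one dose on or after the Week 24 dosing date, and print that n.
- Show TEAEs after Week 24 in earlier stoppers on a separate follow-up line, and keep them in the entire-period table so that every TEAE is accounted for.
- Use only Week 24 to 52 exposure for any second-half rate per 100 patient-years.
- Assign Week 24 itself to one half; both periods now include it.

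The cost is a few sentences, one population flag and one extra table line, with no new data. The downside is that second-half percentages may look slightly less favourable.
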